4.15 Electrocardiogram (ECG)

An ECG will be obtained at baseline A, baseline B and at the twelve (12) month visit.

If the heart failure subject has a historic ECG on file that was completed within 30 days of the assessment date, this may be used for fulfillment of this visit requirement if, in the opinion of the investigator, the historic procedure is highly likely to represent the heart failure subject's current health status.

4.16 **Procedures for Clinical Laboratory Samples**

Laboratory samples will be taken at each REVIVAL visit. All samples will be collected in accordance with acceptable laboratory procedures.

If the heart failure subject has historic laboratory results on file that were drawn within 14 days of the assessment date, these results may be used for fulfillment of a visit requirement if, in the opinion of the investigator, the historic laboratory result(s) are highly likely to represent the subject's current health status.

4.17 Blood for Analysis, Specimen Handling and Storage

The REVIVE-IT Registry will bank samples for those heart failure subjects who consent to participate. From the developed sample bank the goals are to evaluate known biomarkers in this selected advanced heart failure sample and to develop novel biomarkers to improve the prediction of outcomes in subjects with advanced heart failure.

All heart failure subjects who consent to participate will have approximately 8 cc of blood collected for biomarker analysis at baseline B. Heart failure subjects who consent for the genomic analysis biomarkers will have an additional 13 cc collected at baseline B. These specimens will be shipped to the University of Pittsburg Biomarker Core Laboratory as specified in the MOP.

The final selection of biomarkers to be evaluated will be determined following an up to date review of the clinical literature as we approach the end of the study. The biomarkers are likely to include B-type natriuretic peptide, collagen markers (e.g., procollagen types I and III, n-terminal telopeptide, procollagen type I, c-terminal telopeptide, osteopontin, galectin-3), adiponectin, 8-isoprostane, IL-6, soluble receptor of type I alpha-TNF, ST-2, high-sensitivity CRP, CA-125 and troponin.

In addition, DNA banking and genomic analysis will be performed only for heart failure subjects with consent in place to permit the analysis. We will evaluate micro RNAs of prognostic interest in heart failure, such as miR-423-5p. We will genotype all consented heart failure subjects in REVIVAL for a core panel of 10 functional polymorphisms located in genes critical to heart failure progression including: ACE, aldosterone synthase, beta1 adrenergic receptor, alpha adrenergic receptor, NOS3, GNB3, corin (converting enzyme for BNP) and PDE5. At the completion of follow up, genomic analysis will be integrated with the clinical data set and outcomes compared by genotype. Given the role of these genes as targets for heart failure therapeutics, pharmacogenetic interactions will also be explored. In addition to the genotyping

of this core panel, DNA will be banked for analysis of future investigations of innovative genomic markers.

5.0 Study Participation Criteria

5.1 Study Inclusion Criteria

- 1. Ambulatory.
- 2. Chronic systolic heart failure \geq 12 months.
- 3. NYHA II IV for at least 45 of the last 60 days.
- 4. Last documented left ventricular ejection fraction $\leq 35\%$ by any imaging modality.
- 5. Age 18 80 years.
- 6. Currently under the care of a cardiologist at study site.
- 7. On appropriate evidenced -based heart failure medications ACE inhibitor, ARB or sacubitril/valsartan [LCZ-696]; beta blocker; aldosterone antagonist; hydralazine/long-acting nitrate [required of African-American subjects only] for ≥ 3 months absent contraindications or intolerances.
- 8. Has ICD or CRT-D. If CRT-D, present for \geq 3 months.
- 9. Demonstrated advanced heart failure, including any of the following*:
 - i. Serum sodium ≤ 135 mEq/L (obtained as an outpatient)**
 - ii. Serum BNP ≥ 750 pg/mL or NT-proBNP ≥ 3000 pg/mL** (obtained as an outpatient)
 - iii. Seattle Heart Failure Model (SHFM) one year predicted survival ≤ 85%**
 - iv. Heart Failure Survival Score (HFSS) ≤ 7.19**
 - v. Peak VO₂ \leq 55% of predicted for age by Wasserman equation or \leq 14 ml/kg/min, with RER \geq 1.05 ***
 - vi. VE/VC02 slope > 40***
 - vii. 6 minute walk test (6MWT) distance ≤ 350 m without significant noncardiac limitation**
 - viii. Currently listed as Heart Transplant Status II due to heart failure limitation

Or

History of one (1) hospitalization (\geq 24 hours) for acute or acute on chronic heart failure in the past year with additional history to include:

i. Serum BNP ≥ 500 pg/mL or NT-proBNP ≥ 2000 pg/mL** (obtained as an outpatient)

Or

History of two (2) hospitalizations (\geq 24 hours) for acute or acute on chronic heart failure in the past year.

* Qualifying measure must be the most recent of that type of measure obtained (i.e., a $BNP \ge 1000$ obtained 2 months prior would not qualify the heart failure subject if a more recent BNP was < 1000)

**Using values obtained within the prior 90 days, except for peak VO₂ within 365 days

- 10. Willingness to continue to receive heart failure care from the enrolling advanced heart failure clinic over the next two (2) years and to come for all scheduled study visits.
- 11. Written Informed consent given.

5.2 Study Exclusion Criteria

- 1. Known serious medical problem other than heart failure that would be expected to limit 2-year survival (≥50% mortality within 2 years from non-heart failure diagnosis).
- 2. Patient is not likely to be compliant with the protocol, in the opinion of the Investigator.
- 3. Currently hospitalized.
- 4. Current use of an intravenous inotrope.
- 5. Primary functional limitation from non-cardiac diagnosis even if not likely to limit survival.
- Chronic hemodialysis or peritoneal dialysis or serum creatinine value of ≥ 3 mg/dL at time of enrollment.
- 7. Cardiac amyloidosis, cardiac sarcoidosis, constrictive pericardial disease, active myocarditis or congenital heart disease with significant structural abnormality.
- 8. Hypertrophic cardiomyopathy unless dilated LV and no outflow gradient.
- 9. Cardiac conditions that are amenable to surgical or percutaneous procedures (other than VAD or transplant) that would substantially improve prognosis and for which this subject is a reasonable candidate, regardless of whether the procedure will or will not be performed.
- 10. Uncorrected hyperthyroidism or hypothyroidism.
- 11. Pregnancy.

IMPORTANT NOTE: Patients who are currently enrolled (or may wish to enroll in the future) in additional observational studies or clinical trials are **not** excluded from REVIVAL.

5.3 Criteria for Discontinuation or Withdrawal of a Subject

The primary reason for discontinuation or withdrawal of the heart failure subject from the study should be noted using the following categories.

- Lost to follow-up: The heart failure subject did not return to the clinic and attempts to contact the heart failure subject were unsuccessful. All attempts to contact the heart failure subject will be documented.
- Voluntary withdrawal: The heart failure subject (or heart failure subject's legally acceptable representative) wishes to withdraw from the study. The reason for withdrawal, if provided, will be recorded in the electronic case report form (eCRF).
- Study termination: The sponsor, institutional review board (IRB), ethics committee (EC), or regulatory agency terminates the study.
- Other.

The clinical investigator should document in the research record each instance of a heart failure subject's withdrawal including but not limited to 1) whether the withdrawal of the heart failure

subject resulted from a decision by the subject or by the investigator and the reason(s) for the withdrawal, if known. The clinical investigator should also document whether the withdrawal was from all components of the research study or would allow follow-up for clinical outcomes at Month 24. See the Manual of Procedures (MOP) for further details.

Known events/outcomes collected for REVIVAL up to the time of termination should be reported on the study eCRFs. See the MOP for further details.

6.0 Schedule of Observations and Procedures

6.1 Screening and Eligibility Assessment

Historic data must be utilized to identify potential heart failure subjects for the REVIVE-IT Registry. Historic data utilized should be verified on the day of planned consent to ensure that the potential heart failure subject continues to meet inclusion criteria. Written informed consent must be provided by the subject prior to any study procedures being conducted, including screening labs or tests of any kind. All heart failure subjects must consent for blood storage for non-genetic biomarkers to qualify for REVIVAL. Genetic biomarker testing will have a standalone consent. Heart failure subjects who do not consent for the genetic biomarker testing remain eligible to participate in REVIVAL.

6.2 Study Procedures and Assessments

6.2.1 Baseline A

Initiation of baseline A will occur with the heart failure subject signing the Informed Consent document(s). Standard of Care (SOC) testing will be included in the heart failure subject evaluation for this visit. All SOC procedures are labeled as such below. All other procedures will be research expenses. After signing the informed consent document(s), subjects will undergo the following testing and evaluation:

- 1. Directed history and physical (including NYHA and INTERMACS Patient Profile)
- 2. ECG (SOC)
- 3. Blood draw for:
 - a. CBC with platelets and differential count [SOC]
 - b. Comprehensive metabolic panel [SOC]
 - c. Uric Acid
 - d. Total cholesterol
 - e. INR
- 4. Handgrip strength (by dynamometer)
- 5. Gait Speed Test
- 6. 6 minute walk test
- 7. Quality of life and health utility questionnaires
- 8. Patient preference questionnaire
- 9. Caregiver participation overview with heart failure subject
- 10. Dispense patient diary

If the heart failure subject has an historic ECG on file that was completed within 30 days of the assessment date, this may be used for fulfillment of this visit requirement if, in the opinion of the investigator, the historic ECG is highly likely to represent the subject's current health status.

If the heart failure subject has historic laboratory results on file that were drawn within 14 days of the assessment date, these results may be used for fulfillment of this visit requirement if, in the opinion of the investigator, the historic laboratory result(s) are highly likely to represent the subject's current health status.

Baseline A procedures should be completed within two weeks of consent. The baseline B visit should be scheduled to occur two (2) months (\pm 30 days) after consent.

6.2.2 Baseline B

Standard of Care [SOC] testing will be included in the heart failure subject evaluation for this visit. All SOC procedures are labeled as such below. For the baseline B visit, subjects will undergo the following testing and evaluation:

- 1. Directed history and physical (including NYHA and INTERMACS Patient Profile)
- 2. ECG [SOC]
- 3. Blood draw for:
 - a. CBC with platelets and differential count [SOC]
 - b. Comprehensive metabolic panel [SOC]
 - c. Uric Acid
 - d. Total cholesterol
 - e. INR
- 4. Blood draw for Biomarker Analysis (including genetic biomarker testing ONLY if the subject consent is in place)
- 5. Transthoracic Echocardiogram
- 6. Handgrip strength (by dynamometer)
- 7. Gait Speed Test
- 8. 6 minute walk test
- 9. Maximal treadmill cardiopulmonary exercise test (as defined in REVIVAL MOP)
- 10. Quality of life and health utility questionnaires
- 11. Patient preference questionnaire
- 12. Caregiver consent (see MOP for details)
- 13. Obtain information needed to complete follow up eCRF
- 14. Outcome assessments for:
 - Hospitalizations
 - Stroke
 - MCSD
 - Transplant
 - Death (Cardiovascular related vs. Non-cardiovascular related)

If the heart failure subject has an historic ECG on file that was completed within 30 days of the assessment date, this may be used for fulfillment of this visit requirement if, in the opinion of the investigator, the historic ECG is highly likely to represent the subject's current health status.

If the heart failure subject has historic laboratory results on file that were drawn within 14 days of the Baseline B assessment date, these results may be used for fulfillment of this visit requirement if, in the opinion of the investigator, the historic laboratory result(s) are highly likely to represent the subject's current health status.

Core Laboratory Data Handling and Transfer (refer to MOP)

Following completion of the echocardiogram and cardiopulmonary exercise test, studies will be submitted for analysis by the Echocardiography Core Laboratory or Cardiopulmonary Exercise Core Laboratory.

Following completion of baseline B assessments, heart failure subjects will progress to the follow up phase of REVIVAL, with in-clinic follow up visits planned at six (6) months, twelve (12) months, eighteen (18) months and twenty four (24) months.

6.2.3 Six (6) Month Follow up (+/- 45 days)

Standard of Care [SOC] testing will be included in the heart failure subject evaluation for this visit. All SOC procedures are labeled as such below. For the six (6) month follow up visit, subjects will undergo the following testing and evaluation:

- 1. Directed history and physical (including NYHA and INTERMACS Patient Profile)
- 2. Blood draw for:
 - a. CBC with platelets and differential count [SOC]
 - b. Comprehensive metabolic panel [SOC]
- 3. Handgrip strength (by dynamometer)
- 4. Gait Speed Test
- 5. 6 minute walk test
- 6. Quality of life and health utility questionnaires
- 7. Caregiver questionnaire collection (if applicable)
- 8. Obtain information needed to complete follow up eCRF
- 9. Outcome assessments for:
 - Hospitalizations
 - Stroke
 - MCSD
 - Transplant
 - Death (Cardiovascular related vs. Non-cardiovascular related)

If the heart failure subject has historic laboratory results on file that were drawn within 14 days of the assessment date, these results may be used for fulfillment of this visit requirement if, in the opinion of the investigator, the historic laboratory result(s) are highly likely to represent the subject's current health status.

6.2.4 Twelve (12) Month Follow up (+/- 45 days)

Standard of Care [SOC] testing will be included in the heart failure subject evaluation for this visit. All SOC procedures are labeled as such below. For the twelve (12) month follow up visit, heart failure subjects will undergo the following testing and evaluation:

- 1. Directed history and physical (including NYHA and INTERMACS Patient Profile)
- 2. ECG [SOC]
- 3. Blood draw for:
 - a. CBC with platelets and differential count [SOC]
 - b. Comprehensive metabolic panel [SOC]
 - c. Uric Acid
 - d. Total cholesterol
 - e. INR
- 4. Handgrip strength (by dynamometer)
- 5. Gait Speed Test
- 6. 6 minute walk test
- 7. Quality of life and health utility questionnaires
- 8. Patient preference questionnaire
- 9. Caregiver questionnaire collection (if applicable)
- 10. Obtain information needed to complete follow up eCRF
- 11. Outcome assessments for:
 - Hospitalizations (Cardiovascular related vs. Non-cardiovascular related; Heart Failure related vs. Non-Heart Failure related) Stroke
 - VAD
 - Transplant
 - Death (Cardiovascular related vs. Non-cardiovascular related)

If the heart failure subject has an historic ECG on file that was completed within 30 days of the assessment date, this may be used for fulfillment of this visit requirement if, in the opinion of the investigator, the historic ECG is highly likely to represent the subject's current health status.

If the heart failure subject has historic laboratory results on file that were drawn within 14 days of the assessment date, these results may be used for fulfillment of this visit requirement if, in the opinion of the investigator, the historic laboratory result(s) are highly likely to represent the subject's current health status.

6.2.5 Eighteen (18) Month Follow up (+/- 45 days)

Standard of Care [SOC] testing will be included in the heart failure subject evaluation for this visit. All SOC procedures are labeled as such below. For the eighteen (18) month follow up visit, heart failure subjects will undergo the following testing and evaluation:

- 1. Directed history and physical (including NYHA and INTERMACS Patient Profile)
- 2. Blood draw for:
 - a. CBC with platelets and differential count [SOC]
 - b. Comprehensive metabolic panel [SOC]
- 3. Handgrip strength (by dynamometer)
- 4. Gait Speed Test
- 5. 6 minute walk test
- 6. Quality of life and health utility questionnaires
- 7. Caregiver questionnaire collection (if applicable)
- 8. Obtain information needed to complete follow up eCRF
- 9. Outcome assessments for:
 - Hospitalizations
 - Stroke
 - MCSD
 - Transplant
 - Death (Cardiovascular related vs. Non-cardiovascular related)

If the heart failure subject has historic laboratory results on file that were drawn within 14 days of the assessment date, these results may be used for fulfillment of this visit requirement if, in the opinion of the investigator, the historic laboratory result(s) are highly likely to represent the subject's current health status.

6.2.6 Twenty-four (24) Month Follow up (+/- 30 days)

Standard of Care [SOC] testing will be included in the heart failure subject evaluation for this visit. All SOC procedures are labeled as such below. For the twenty four (24) month follow up visit, heart failure subjects will undergo the following testing and evaluation:

- 1. Directed history and physical (including NYHA and INTERMACS Patient Profile)
- 2. Blood draw for:
 - a. CBC with platelets and differential count [SOC]
 - b. Comprehensive metabolic panel [SOC]
- 3. Handgrip strength (by dynamometer)
- 4. Gait Speed Test
- 5. 6 minute walk test
- 6. Quality of life and health utility questionnaires
- 7. Patient preference questionnaire
- 8. Caregiver questionnaire collection (if applicable)

- 9. Obtain information needed to complete follow up eCRF
- 10. Outcome assessments for:
 - Hospitalizations
 - Stroke
 - MCSD
 - Transplant
 - Death (Cardiovascular related vs. Non-cardiovascular related)

If the heart failure subject has historic laboratory results on file that were drawn within 14 days of the assessment date, these results may be used for fulfillment of this visit requirement if, in the opinion of the investigator, the historic laboratory result(s) are highly likely to represent the subject's current health status.

7.0 Adverse Event and Unanticipated Problems

7.1 Adverse Event and Unanticipated Problems Reporting Requirements

Only adverse events resulting from research related procedures will be collected for safety purposes from heart failure subjects and caregivers. Additional adverse event data will be collected for outcome data collection purposes, but this data will not meet expedited reporting criteria in any circumstance (Refer to Appendix D).

Investigators **must** notify the REVIVAL DCC within 24 hours of discovering any SAEs or UPs, and to their IRB as dictated by the local IRB policy. All SAEs and UPs must be documented on the appropriate eCRF and submitted to the REVIVAL DCC.

The REVIVAL DCC will provide notification of reported SAEs, AEs and UPs to the required oversight bodies as detailed in the REVIVAL MOP.

7.2 Adverse Event Category Definitions

Adverse Event

An adverse event is formally defined as any undesirable occurrence in a study subject, whether or not it is related to the study. Any condition that was recorded as pre-existing is *not* an AE unless there is a change in the nature, severity or degree of the condition.

For REVIVAL, only adverse events resulting from research related procedures will be collected for safety purposes from Heart Failure subjects and Caregivers. Additional adverse event data will be collected for outcome data collection purposes, but this data will not meet expedited reporting criteria in any circumstance.

Serious Adverse Event

Serious adverse events (SAEs) are defined by FDA regulation as any experience that results in a fatality or is life threatening; results in significant or persistent disability; requires or prolongs a hospitalization; results in a congenital anomaly/birth defect; or represents other significant hazards or potentially serious harm to research subjects or others, in the opinion of the investigators. The REVIVAL definition of hospitalization is any cumulative stay within a hospital or emergency department \geq 24 hours (including time for observation) or any formal admission. Important medical events that may not result in death, be life-threatening, or require hospitalization may be considered a SAE when, based upon appropriate medical judgment, they may jeopardize the subject and may require medical or surgical intervention to prevent one of the outcomes listed in this definition.

Unanticipated Problems (UPs)

An Unanticipated Problem (UP) generally includes any incident, experience, or outcome that meets **all** of the following criteria: (1) Unexpected (in terms of nature, severity, or frequency) given (a) the research procedures that are described in the protocol-related documents, such as the IRB-approved research protocol and informed consent document; and (b) the characteristics of the heart failure subject population being studied; *and* (2) Related or possibly related to participation in the research (*possibly related* means there is a reasonable possibility that the incident, experience, or outcome may have been caused by the procedures involved in the research); *and* (3) Suggests that the research places subjects or others at a greater risk of harm (including physical, psychological, economic, or social harm) than was previously known or recognized.

Based on the definitions above many adverse events are not unanticipated problems, and many unanticipated problems are not adverse events. However, some adverse events are also unanticipated problems. For example, a SAE that is unexpected and at least possibly related to study participation is also by definition an unanticipated problem. As stated above, an unanticipated problem may not necessarily be an adverse event, which is the case when the problem does not cause actual physical harm to participants. For example, if a laptop computer with sensitive, identifiable study data is stolen, this theft places the participants at greater *risk* of psychological or social harm; this is an unanticipated problem that is not an adverse event.

7.3 Causality

The investigator will assess the relationship of an adverse event to the research procedure. Causality will be defined as follows:

Probable

Adverse events that, after careful medical evaluation, are considered with a high degree of certainty to be related to the research procedure. The following characteristics will apply:

- o A reasonable temporal relationship exists between the event and the research procedure/intervention, and
- o The event is a known reaction to the research procedure/intervention, and cannot be explained by an alternative etiology commonly occurring in the population/individual.

Possible

Adverse events that, after careful medical evaluation, do not meet the criteria for a probable relationship to the research procedure, but for which there is evidence to suggest a causal relationship. The following characteristics will apply:

- o The event occurs after research procedure, and
- o The event is not a known reaction to research procedure, but cannot be explained by a commonly occurring alternative etiology.

Unlikely

Adverse events that, after careful medical evaluation, do not meet the criteria for a possible or probable relationship to the research procedure and for which a connection is doubtful but cannot be ruled out. The following characteristics will apply:

- o The event does not follow a reasonable temporal sequence from administration of the research procedure, or
- o May have been produced by environmental factors, and there is no apparent pattern of response to the research procedure.

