10.2 Potential Risk

All heart failure subjects participating in REVIVAL face risks including, but not limited to the following:

- Cardiopulmonary exercise tolerance test: heart attack, irregular heartbeats, or death in 1 out of 10,000 patients.
- 6MWT and Gait Speed Test: chest pain, shortness of breath, dizziness, fatigue, and falling.
- ECG: localized rash or irritation at the location of electrode placement (rare circumstances)
- Echocardiogram: mild discomfort of the probe touching skin
- Blood draws: fainting, pain, bruising and bleeding at the site of the needle stick and rarely, an infection.
- Biomarker sample collection: breach of confidentiality. Significant precautions will be taken to minimize this risk and prevent disclosure of subject identity to unauthorized individuals.

As with any research study, there may be additional risks that are unknown or unexpected.

In the event of unforeseen or increased risks to subjects, suspension or termination of the clinical study shall be considered (Refer to the MOP for subject management instructions in this event).

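### The Section 7.3 causality grades leave no category for a timely known procedure reaction that heart failure could also explain, and no known reaction can ever be graded Possible

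*Protocol*

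**What the plan says.** Section 7.3 of the protocol has three grades. Each has an introductory sentence and a list of features that are stated to apply.

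- **Probable** needs both "A reasonable temporal relationship exists between the event and the research procedure/intervention, and" and "The event is a known reaction to the research procedure/intervention, and cannot be explained by an alternative etiology commonly occurring in the population/individual".
- **Possible** needs both "The event occurs after research procedure, and" and "The event is not a known reaction to research procedure, but cannot be explained by a commonly occurring alternative etiology". Its introductory sentence is wider: it speaks of some evidence of causation in an event that falls short of Probable.
- **Unlikely** needs one of two features: "The event does not follow a reasonable temporal sequence from administration of the research procedure, or" "May have been produced by environmental factors, and there is no apparent pattern of response to the research procedure". Its introductory sentence covers events that fail the other two grades and whose connection is doubtful but not excluded.

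Section 7.2, in the definition of an Unanticipated Problem, says that possibly related "means there is a reasonable possibility that the incident, experience, or outcome may have been caused by the procedures involved in the research". It excludes neither known reactions nor events with another candidate cause.

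Section 10.2 gives the cardiopulmonary exercise test risks as "heart attack, irregular heartbeats, or death in 1 out of 10,000 patients". Section 4.3 places that test at baseline B for consented subjects. Section 7.1 limits safety collection to adverse events that result from research procedures.

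**The concern.** A middle grade normally takes the uncertain cases: events the procedure is known to cause, close in time, where the disease is a rival explanation. Here the middle grade shuts them out twice, once because the reaction is known and once because a rival explanation exists. The top grade shuts them out on the second ground.

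These are foreseeable events in this cohort. Section 10.2 names irregular heartbeats and death as exercise-test risks. Section 1.1 describes mortality and morbidity in systolic heart failure as high, and Appendix B says recurrent ventricular tachyarrhythmias can dominate the clinical picture. The same pattern arises for milder events: Section 10.2 lists shortness of breath and fatigue for the walk and gait tests, and Appendix C defines NYHA classes by those symptoms.

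At stake is whether harm from a research procedure is recorded as such. Safety collection depends on an event being regarded as procedure-related, and investigators would have no consistent way to grade such cases.

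**Working it through.** The protocol gives no figure for this point, so the main check is one of logic.

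**Step 1. Facts used by the definitions (all from Section 7.3).**
- T: the event is timely after the procedure.
- K: it is a known reaction.
- A: a commonly occurring alternative etiology can explain it.
- E: environmental factors may have produced it and there is no pattern of response.

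**Step 2. The grades as rules.**
- Probable = T and K and not A
- Possible = T and not K and not A
- Unlikely = not T, or E

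Possible strictly asks only that the event comes after the procedure. Coding that as T does not affect the rows at issue, all of which are timely.

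**Step 3. All 16 combinations.**

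| T | K | A | E = no | E = yes |
|---|---|---|---|---|
| yes | yes | no | Probable | Probable and Unlikely |
| yes | yes | yes | **none** | Unlikely |
| yes | no | no | Possible | Possible and Unlikely |
| yes | no | yes | **none** | Unlikely |
| no | either | either | Unlikely (4 rows) | Unlikely (4 rows) |

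Results:
1. In no row with K = yes is Possible available.
2. A timely known reaction with a common alternative explanation fails Probable on A and Possible on both K and A. Without environmental factors it has no category.
3. A timely event that is not a known reaction but has a common alternative explanation also has no category.
4. Where two grades fit, the introductory sentence of Unlikely settles it, because it applies only to events that fail the other two.

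**Step 4. Comparison with Section 7.2.** The event in result 2 can satisfy the reasonable-possibility test in Section 7.2 and still be barred from Possible in Section 7.3. It can also satisfy the introductory sentence of Possible while failing its listed features, so Section 7.3 conflicts with itself.

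**Step 5. Size.** Inputs: at most 400 subjects (Section 3.1), one exercise test each (Appendix A), and a risk of 1 in 10,000 (Section 10.2). I assume that this risk covers the three named events together; if it refers to death alone, the figures below apply to deaths only.
- Expected events: 400 × 0.0001 = 0.04
- Chance of at least one: 1 − (1 − 0.0001)^400 = 0.039, or 3.9%

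Both are upper bounds at that risk, because 400 is a ceiling and subjects lost before baseline B are not tested.

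**Step 6. What one event would show.** The exact two-sided 95% lower limit for 1 event in 400 solves 1 − (1 − p)^400 = 0.025. This gives p = 1 − 0.975^(1/400) = 0.000063, about 0.63 per 10,000. That lies below the quoted 1 per 10,000, so the interval does not exclude the quoted risk.

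**The case against.** The strongest reply is that the gap is a drafting flaw with limited reach. Several parts of that reply stand.

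- **Probable is not closed to exercise-test events.** Whether a common alternative explains the event is left to the investigator's medical evaluation. An arrhythmia at peak effort may be judged not otherwise explained, and Probable is then available. A reader might infer that the named exercise-test risks can never be graded as related; the text supports that only for Possible.
- **Not every named risk is shown to fall in the gap.** The documents describe background mortality and arrhythmia, but do not say that heart attack is common in this population.
- **The Unanticipated Problem route is separate.** Section 7.2 has its own relatedness test and does not refer to the Section 7.3 grades.
- **Other routes record the event.** Section 7.1 asks for notice of any serious adverse event within 24 hours. Deaths and hospitalizations are collected as outcomes whatever their cause (Section 3.2, Appendix D).
- **No passage ties a Section 7.3 grade to collection, to monitoring-board reporting or to the Section 10.2 review of risk.** A reader might infer that such events are downgraded to Unlikely and vanish from safety oversight. The documents do not say so, and a timely reaction does not meet the listed features of Unlikely.

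What the reply does not remove is the gap. Outcome data are excluded from expedited reporting (Section 7.1, Appendix D), so a death or hospitalization recorded only there carries no attribution to the procedure. The wide introductory sentence of Possible does not help either, since its listed features are stated to apply and are joined by *and*.

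**Conclusion.** The point holds as a defect in the definitions. No known reaction can be graded Possible, and two of the 16 combinations have no grade: timely events with a common alternative explanation and no environmental factors, whether or not the reaction is known. Section 7.3 therefore conflicts with Section 7.2 and with its own introductory sentence for Possible.

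The consequence is possible under-attribution of procedure-related events, with partial protection from the routes listed above. Systematic loss of such events is not shown. With at most 0.04 expected serious exercise-test events, each attribution counts, but a single event would not by itself establish that the risk exceeds the quoted figure.

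This should be fixed, but no objective, endpoint or analysis of the registry depends on it. The conclusion assumes that the listed features are binding, as their wording indicates, and that risks named in Section 10.2 count as known reactions.

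**What to change.** In Section 7.3, reconcile Possible with Section 7.2. Delete the condition that the event is not a known reaction, and delete the requirement that no common alternative etiology can explain it. Possible would then cover events that follow the research procedure, fall short of Probable, and have a reasonable possibility of having been caused by it. Leave the Probable standard as it is. Both empty rows in the table then have a grade whenever causation is reasonably possible.

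In the same edit, check that the listed features of Unlikely can take a timely event for which causation is not reasonably possible; its introductory sentence already suits such an event.

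The cost is a few lines of protocol text, the matching eCRF guidance, and slightly more events graded Possible.
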